11.2. ANALYSIS POPULATIONS

It is expected, that during this clinical investigation only one population for T2 Alpha Tibia will exist and all subjects will be analyzed "Per Protocol" (PP). However, it cannot be fully avoided that in theory subjects might need to be excluded from the PP population. In this occasion, there will be two groups being fully analyzed to ensure transparency and avoid bias.

The groups are defined as follows:

Intent-to Treat Population

The Intent-to-Treat (ITT) Population is defined to be all enrolled subjects. An enrolled subject is a subject that has signed informed consent, all screening procedures have been successfully completed, is eligible and can receive treatment. The ITT population will not be analyzed for the annual reports and will only be included in the final report.

Per Protocol Population

The Per Protocol (PP) Population is defined to be all subjects in the ITT Population with no major protocol violations. The protocol violations that will exclude a subject are as follows:

• The subject does not receive the Tibial Nail of the T2 Alpha Tibia Nailing System

. .

- The subject does not meet all eligibility criteria
- The subject has a protocol violation that is considered likely to affect subject outcomes.

After the clinical investigation has been completed, a review of the data will be conducted to determine which subjects are to be excluded from the PP population.

11.3. ANALYSIS PLAN BY CLINICAL INVESTIGATION ELEMENT AND EVALUATION

11.3.1. Statistical Analysis

Evaluation elements are defined as the questions on the CRF/eCRF. The SAP lists all evaluation elements and secondary elements which will be based on calculations between two or more evaluation elements.

All quantitative variables, including those based on calculations (secondary elements), will be analyzed with a case summary evaluation before the detailed characteristics and parameter can be evaluated. A case summary contains a listing of the number of valid cases/values, missing cases/values (if any) and total cases/values in the specific analysis. In general, as central position parameter for quantitative variables the mean, median and mode will be analyzed. As variation parameter the standard deviation, 95% confidence interval of the mean, interquartile range and range (based on maximum and minimum) will be calculated. All quantitative variables will be assessed for normality used the Shapiro-Wilk test. For optional visualization of quantitative variables, box-and-whisker plots will be used. Additional analyses like skewness and kurtosis measures of standard errors are also optional.

All qualitative variables, including those based on summaries (secondary elements), will be analyzed listing the proportions, frequencies, column and row totals and missing proportion (if any).

The SAP reflects this approach and specifies the variables characteristics (quantitative or qualitative) in detail together with the related analysis strategy. This also includes calculation and summaries based on primary elements and the required analysis.

11.3.2. Primary Analysis / Endpoint

This analysis is only part of the final report. The primary endpoint analysis will only be executed once at the end of the clinical investigation and will not be part of any interim or annual reports or presentations given in front of the final report.

The 12 months post-operative results for subjects implanted with the T2 Alpha Tibia Nailing System will be compared to Sanders et al: Semiextended intramedullary nailing of the tibia using a suprapatellar approach: radiographic results and clinical outcomes at a minimum of 12 months follow-up. J Orthop Trauma, 2014; Sun et al: The outcome comparison of the suprapatellar approach and infrapatellar approach for tibia intramedullary nailing. Int Orthop, 2016; and Chan et al: Suprapatellar Versus Infrapatellar Tibial Nail Insertion: A Prospective Randomized Control Pilot Study. J Orthop Trauma, 2016". Specifically, the SF-36 score results reported by Wang, et al. (2017), Sanders, et al. (2014), Sun, et al. (2016) and Chan, et al. (2016) will serve as the control groups for the T2 Alpha Tibia group.

Higher SF-36 PCS and MCS score results are linked to better subject results and vice versa.

The clinical investigation endpoint is non-inferiority to the control, meaning the clinical investigation result should be equal or better than the control. In this clinical investigation, an equal or better SF-36 score result means equal or greater (\geq). As only results from samples will be captured, results are mostly estimates of the true population parameter. These estimates vary by a certain area, where it is expected that the true population parameter falls within. Based on this, it is required to specify a lower limit for the acceptable difference or zone of indifference, denoted as $-\theta$.

Hypotheses were developed to allow for a comparison of the 12 months post-operative SF-36 PCS to evaluate effectiveness / performance. The 12 months post-operative SF-36 PCS is the primary endpoint of this clinical investigation. Hypothesis tests will be one-sided with a significance level α of 5%.

Hypothesis	Equations		Interpretation		
Null (H ₀) $A - B < -\theta$ $T2 \text{ Alpha Tibia (A)} - Co$ $pooled \text{ benchmark result}$		` '	Central tendency of A is inferior to the central tendency of B.		
Alternative (H ₁)	A – B ≥ -θ T2 Alpha Tibia (A) – 0 pooled benchmark res	,	Central tendency of A is non-inferior to the central tendency of B.		
95% H ₀ H ₁					
Possible Evidence (p)	Possible Decisions	Possible Co	onclusions – SF-36 PCS		
p-value > α (0.05) Fail to reject null hypothesis (H ₀)		T2 Alpha Tibia < Control (pooled benchmark results) Insufficient evidence to reject the null hypothesis (H ₀ : A – B < -θ) at the pre-determined significance level of 5%.			
p-value $\leq \alpha$ (0.05) Reject null hypothesis (H ₁)		results) Sufficient e	ibia ≥ Control (pooled benchmark vidence to reject the null hypothesis (-θ) at the pre-determined significance.		

To test non-inferiority, the 12 months mean SF-36 PCS result of the T2 Alpha Tibia group will be compared to the mean estimate of the control group, 43.48 points.

To be able to identify an acceptable difference or zone of indifference (-θ), the lower 90% confidence interval (CI) of the SF-36 PCS result at 12 months post-operative in the control group (Sanders, et al.; Sun, et al.; Chan, et al.) was used as lower limit (lower 90% CI of control is 39.25 points). The maximum acceptable difference in the negative direction is 4.23 points.

Based on the underlying distribution of the data and the result of the normality assessment, either the parametric one-sample t-test or the non-parametric one-sample sign test will be used to compare the 12 months post-operative SF-36 PCS result of the T2 Alpha Tibia group against the value of 39.25 points (mean of control - θ or 43.48 - 4.23 = 39.25 points).

5 10 00

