3.1.1. Primary Analysis / Endpoint

This analysis is only part of the final report. The primary endpoint analysis will only be executed once at the end of the clinical investigation and will not be part of any interim or annual reports or presentations given in front of the final report.

The 12 months post-operative results for subjects implanted with the T2 Alpha Tibia Nailing System will be compared to Sanders et al: Semiextended intramedullary nailing of the tibia using a suprapatellar approach: radiographic results and clinical outcomes at a minimum of 12 months follow-up. J Orthop Trauma, 2014; Sun et al: The outcome comparison of the suprapatellar approach and infrapatellar approach for tibia intramedullary nailing. Int Orthop, 2016; and Chan et al: Suprapatellar Versus Infrapatellar Tibial Nail Insertion: A Prospective Randomized Control Pilot Study. J Orthop Trauma, 2016". Specifically, the SF-36 score results reported by Wang, et al. (2017), Sanders, et al. (2014), Sun, et al. (2016) and Chan, et al. (2016) will serve as the control groups for the T2 Alpha Tibia group.

Higher SF-36 PCS and MCS score results are linked to better subject results and vice versa.

The clinical investigation endpoint is non-inferiority to the control, meaning the clinical investigation result should be equal or better than the control. In this clinical investigation, an equal or better SF-36 score result means equal or greater (\geq). As only results from samples will be captured, results are mostly estimates of the true population parameter. These estimates vary by a certain area, where it is expected that the true population parameter falls within. Based on this, it is required to specify a lower limit for the acceptable difference or zone of indifference, denoted as - θ .

Hypotheses were developed to allow for a comparison of the 12 months post-operative SF-36 PCS to evaluate effectiveness / performance. The 12 months post-operative SF-36 PCS is the primary endpoint of this clinical investigation. Hypothesis tests will be one-sided with a significance level α of 5%.

Hypothesis	Equations	Interpretation	
Null (H ₀)	$A - B < -\theta$	Central tendency of A is inferior to	
	12 Alpha 11bia (A) – Control (B, pooled benchmark results) < $-\theta$	the central tendency of B.	
Alternative	$A - B \ge -\theta$	Central tendency of A is non-inferi	
(H ₁)	T2 Alpha Tibia (A) - Control (B, pooled benchmark results) $\geq -\theta$	to the central tendency of B.	

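### The Protocol 11.3.2 decision table heads a non-significant result as worse than control, and heads a pass as at least equal to control without the 4.23-point margin

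*Protocol*

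**What the plan says.** Protocol 11.3.2 and SAP 3.1.1 set a one-sided 5% test of the 12-month SF-36 PCS. The null is that T2 Alpha Tibia minus control lies below −θ. The control value is 43.48, and "The maximum acceptable difference in the negative direction is 4.23 points", so the test value is 39.25. Depending on the normality assessment, "either the parametric one-sample t-test or the non-parametric one-sample sign test will be used", in both cases against 39.25. The Protocol's hypothesis table reads the alternative as "Central tendency of A is non-inferior to the central tendency of B", and SAP 3.1.1 has the same reading.

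The Protocol then adds a table that turns the p-value into a conclusion. The p > 0.05 cell reads "T2 Alpha Tibia < Control (pooled benchmark results) Insufficient evidence to reject the null hypothesis", and goes on to cite the null with −θ. The p ≤ 0.05 cell is partly broken in the text version, but its heading is legible ("ibia ≥ Control (pooled benchmark"). The sentence below it speaks of sufficient evidence to reject the same null. Neither heading mentions the margin. The table does not appear in the SAP text.

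On a separate matter, the software output reproduced in Protocol 11.1 and SAP 3.2 gives an expected precision for the mean of plus or minus 2.77 points and labels it 95% confidence.

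**The concern.** A non-significant non-inferiority test is inconclusive: it does not show that the device is worse than the benchmark. The p > 0.05 heading says that it is, and the sentence in the same cell contradicts it. A significant test shows a mean (or a median, if the sign test is used) above 39.25. It does not show a mean at or above 43.48, which is what the p ≤ 0.05 heading says if taken literally.

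The primary analysis is run once, for the final report, and this table supplies its conclusion. If the headings are carried into the report, an inconclusive trial is reported as an inferior device, and a pass with an observed mean below 43.48 is reported as at least equal to control. Only the stated conclusion is at risk. The sentences under the headings, the full test output required by SAP 6.6 and the 95% confidence interval in SAP Table 6.5.2 would still show the actual result.

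The precision label matters less. A reader who takes ±2.77 as a two-sided 95% figure will expect a narrower interval than the 95% interval of the mean that SAP 4.7 and Table 6.5.2 commit to reporting.

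**Working it through.** **Inputs.** From Protocol 11.1 and SAP 3.2: n = 61, planning SD 13.04, assumed true mean 43.48, test value 39.25, one-sided α = 0.05, benchmark SE 1.985. The SD actually reported by one benchmark source is 6.52 (infrapatellar subgroup), which the plan doubled. As in the plan, 43.48 is treated as a fixed constant unless stated.

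**1. The plan's own power.** SE = 13.04/√61 = 1.670. Noncentrality = (43.48 − 39.25)/1.670 = 2.53. With t(0.95, 60) = 1.6706, noncentral-t power is 0.805, matching the SAP 3.2 software output.

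**2. What a pass shows.** Lowest passing mean = 39.25 + 1.6706 × SE, taking the observed SD as given:

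| SD | SE | Lowest passing mean | Below 43.48 by |
|---|---|---|---|
| 13.04 | 1.670 | 42.04 | 1.44 |
| 6.52 | 0.835 | 40.64 | 2.84 |

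With the sign test at n = 61 (no ties), a pass needs at least 38 values above 39.25: P(X ≥ 38) = 0.036, whereas P(X ≥ 37) = 0.062. That result concerns the median, while 43.48 is a mean.

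**3. What a non-pass shows.** At SD 13.04, an observed mean is itself significantly below 43.48 (one-sided 5%) only if it is under 43.48 − 1.6706 × 1.670 = 40.69. Observed means from 40.69 to 42.04 therefore fail against 39.25 and would be headed as below control, although they are not significantly below 43.48.

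**4. Which interval agrees with the test.** The t-test passes exactly when the one-sided 95% lower limit exceeds 39.25. The two-sided 95% interval uses t(0.975, 60) = 2.0003, so its lower limit exceeds 39.25 only from an observed mean of 39.25 + 2.0003 × 1.670 = 42.59. Observed means from 42.04 to 42.59 pass the test with a two-sided 95% lower limit below 39.25. At 42.04 that limit is 42.04 − 3.34 = 38.70. If the true mean is 43.48, this happens in 0.805 − 0.703 = about 10% of trials, where 0.703 is the power at one-sided 2.5%.

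**5. The precision label.** The plan says that its figure is a median precision. The median sample SD is 13.04 × √(median χ²₆₀/60) = 13.04 × 0.9944.
- Two-sided 90%: 1.6706 × 1.670 × 0.9944 = 2.77.
- Two-sided 95%: 2.0003 × 1.670 × 0.9944 = 3.32.

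The software limits in SAP 3.2 agree with the first: (46.25 − 40.71)/2 = 2.77, or 1.66 SE. The stated figure is 2.774/3.321 = 0.835 of the two-sided 95% figure, about 16% narrower.

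**The case against.** **The ≥ sign is declared shorthand.** The acceptance criteria in Protocol 11.1 label the non-inferiority path with the same symbol, and 11.3.2 says that the endpoint is non-inferiority, with equal or better meaning equal or greater. The hypothesis table gives the margin, the sentence in the same cell refers to −θ, and the text after the table gives 4.23 and 39.25. This stands as an explanation: the p ≤ 0.05 heading is incomplete, not a claim of a different test. It does not rescue the p > 0.05 heading, since no shorthand turns insufficient evidence into inferiority.

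**The harm is conditional.** It needs someone to copy the headings without the sentences below them, and SAP 6.6 asks for the test output, not the headings. This also stands, and it limits the point to the stated conclusion.

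**Stronger readings that a reader might infer, and that the documents do not support:**
- *A pass could be significantly below the benchmark.* At SD 6.52 the upper one-sided 95% limit at the lowest passing mean is 40.64 + 1.39 = 42.04 after rounding, which is below 43.48. That treats 43.48 as known exactly. With the benchmark SE included, the gap is 2.84/√(0.835² + 1.985²) = 1.32 combined SE, and at SD 13.04 it is 1.44/√(1.670² + 1.985²) = 0.56. Neither reaches one-sided 5%.
- *The wording causes a 19.5% error.* A device truly at 43.48 would fail in 1 − 0.805 = 19.5% of trials under any wording. This is the planned type II error, and it is 0.04% at SD 6.52.
- *The definition of the endpoint is also wrong,* because it says "meaning the clinical investigation result should be equal or better than the control". The same paragraph goes on to say that "it is required to specify a lower limit for the acceptable difference or zone of indifference", so the margin is supplied there.

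**The precision label is a separate matter.** It sits in other sections and has no effect on n or power. Protocol 11.1 also states that a two-sided 90% interval corresponds to a one-sided 95% one. Both are correct, but a plus-or-minus figure describes a two-sided interval, so the label still needs correcting as a minor item.

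**Conclusion.** The point holds as a wording fault in one table of the Protocol. The p > 0.05 heading is wrong as written and contradicts its own cell. The p ≤ 0.05 heading is recognisable shorthand but omits the margin: at n = 61 and SD 13.04 it would cover observed means down to 42.04, and at SD 6.52 down to 40.64. These limits assume the t-test, 61 evaluable subjects and an observed SD equal to the stated value. Nothing here shows a fault in the test, margin, sample size or power, and the stated power reproduces. The precision label is a separate minor error: 2.77 where a two-sided 95% figure would be 3.32. The correction should be made before the final report is written, since that is the only place where the primary conclusion will appear.

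**What to change.** In the Protocol 11.3.2 decision table, replace the two headings:
- p > 0.05: non-inferiority not demonstrated.
- p ≤ 0.05: non-inferior to the benchmark within 4.23 points, with the 12-month PCS mean (median, if the sign test is used) above 39.25.

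If an interval is shown against 39.25 alongside the t-test, use the one-sided 95% lower limit, which equals the two-sided 90% lower limit and is the interval that Protocol 11.1 says will be applied. The two-sided 95% interval of the mean can stay as a descriptive result, but should not be set against 39.25 as the criterion.

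Separately, in Protocol 11.1 and SAP 3.2, relabel ±2.77 as two-sided 90% (one-sided 95% limits), or restate it as ±3.32 at two-sided 95%.

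The cost is two headings in the Protocol and one label in each document. The stated precision changes from 2.77 to 3.32 only if it is restated rather than relabelled.

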11.1. DETERMINATION OF SAMPLE SIZE

The 12 months post-operative results for subjects implanted with the Tibial Nail of the T2 Alpha Tibia Nailing System will be compared to a historical group and results reported by Wang, et al. (2017); Sanders, et al. (2014); Sun, et al. (2016); and Chan, et al. (2016) will serve as the control group for the T2 Alpha Tibia Nail subjects.

Hypotheses were developed to allow for a comparison of 12 months post-operative SF-36 Physical Component Summary (PCS) results and 12 months effectiveness/performance between these two populations.

Benchmark and Objectives for Planned Research				
Endpoint Non-inferiority related to the SF-36 Physical Component Summary (PCS) for subject undergoing infrapatellar (IP) and/or suprapatellar (SP) tibia nailing at 12 months post operative compared to the pooled literature control.				
Estimated drop- out rate	20% Source: "Stannard et al: Functional Outcome Following Intramedullary Nailing of the Femur. A Prospective Randomized Comparison of Piriformis Fossa and Greater Trochanteric Entry Portals JBJS 2011" Stannard et al. reported a lost to follow up rate of 19.6% (11/56). Note: The source of Stannard et al. was used for T2 Alpha Tibia as well as it represents a worst-case drop-out rate.			

Results as reported by Benchmark

Non-inferiority related to the SF-36 Physical Component Summary (PCS) for subjects undergoing infrapatellar (IP) or suprapatellar (SP) tibia nailing at 12 months post-operative.

The results from the sources Chan et al, Sanders et al., and Sun et al. were pooled to determine overall two-sided 90% confidence intervals of the mean SF-36 PCS (physical) and mean SF-36 MCS (mental) scores.

Note: The results reported by Wang et al. seemed to be based on a different calculation method for the determination of the SF-36 scores and it was not possible to evaluate, what exactly was done by the authors. The score values reported by Wang et al. are much higher compared to what was normally reported in the literature and what was defined in country specific weights and coefficients. Wang et al. reported median score values whereas the other authors reported means. As summary score results usually tend to deviate from normality, means and medians might differ significantly. Therefore, the results reported by Wang et al. were not included into the pooled analysis.

Source	Subgroup	Mean SF36- PCS	Mean SF36- MCS	Pooling
Chan et al.	IP	38.00	47.00	included

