Chan et al.	SP	46.00	47.00	included
Sanders et al.	SP	40.80	46.00	included
Sun et.al.	SP	49.41	44.71	included
Sun et.al.	IP	43.21	43.81	included
Wang et.al.		79.10	77.00	excluded

Summary of explorative analysis is listed below:

18215 54 30

			Statistic	Std. Error
SF-36 PCS Physical at 12	Mean		43,4840	1,98495
months post-op	90% Confidence Interval	Lower Bound	39,2524	
	for Mean	Upper Bound	47,7156	
	Median		43,2100	
	Std. Deviation		4,43849	
	Minimum		38,00	
	Maximum		49,41	
	Range		11,41	
	Interquartile Range		8,31	
SF-36 PCS Mental at 12	Mean		45,7040	,63333
months post-op	90% Confidence Interval for Mean	Lower Bound	44,3538	
		Upper Bound	47,0542	
	Median		46,0000	
	Std. Deviation		1,41617	
	Minimum		43,81	
	Maximum		47,00	
	Range		3,19	
	Interquartile Range		2,74	

As the mean physical score (PCS) was slightly lower, it was used for the sample size calculation.

For the clinical investigation the one-sided 95% confidence interval will be applied.

Acceptance Criteria for Sample Size Calculation					
Significance Level (α)	0.05 (5%)				
Power (1-β)	0.80 (80%)				
Confidence Interval (CI)	0.95 (95%)				
Tails	1				
Path	Non-inferiority T2 Alpha Tibia (A) ≥ Benchmark (B, pooled benchmark results)				
Hamathagas Dain	Null (H ₀)	$A - B < -\theta$			
Hypotheses Pair	Alternative (H ₁)	$A - B \ge -\theta$			
Benchmark Timepoint	12 months post-operative				
Benchmark Mean	43.48 points SF-36 PCS at 12 months (IP an	d SP together)			
Benchmark Std. Dev.	No standard deviation results were given by Chan et al., Sanders et al. nor b Wang et al. Only Sun et al. reported standard deviations at 12 months postoperative for SF-36 PCS of 6.27 for the SP and of 6.52 for the IP subgroup As a worst-case, the double standard deviation reported by Sun et al. was used for the sample size calculation (2 * 6.52 = 13.04 points)				
Benchmark 90% CI of Mean	Lower 90% CI: 39.25 (two-sided 90% CI equals a one-sided 95% CI)				
Denchmark 90% CI of Mean	Upper 90% CI: 47.72				
Margin (-θ)	Lower 90% CI of Benchmark: 39.25				
Software Used	IBM SPSS Sample Power V3.0				

IBM SPSS Sample Power Output

One goal of the proposed clinical investigation is to test the null hypothesis that the population mean is 39.25. The criterion for significance (alpha) has been set at 0.050. The test is 1-tailed, which means that only an effect in the expected direction will be interpreted.

[figure not shown]

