With the proposed sample size of 61 subjects, the clinical investigation will have power of 80.0% to yield a statistically significant result.

This computation assumes that the population from which the sample will be drawn has a mean of 43.48 with a standard deviation of 13.04. The observed value will be tested against a theoretical value (constant) of 39.25.

This effect was selected as the smallest effect that would be important to detect, in the sense that any smaller effect would not be of clinical or substantive significance.

A second goal of this clinical investigation is to estimate the mean in the population. On average, a clinical investigation of this design would enable us to report the mean with a precision (95.0% confidence level) of plus/minus 2.77 points.

The precision estimated here is the median precision. Precision will vary as a function of the observed standard deviation (as well as sample size), and in any single clinical investigation will be narrower or wider than this estimate.

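### The normality result decides whether the primary test concerns a mean or a median, yet the limit of 39.25 and the sample size were built only for the mean

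*Protocol*

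**What the plan says.** CIP 11.3.2 frames the comparison in means: "the 12 months mean SF-36 PCS result of the T2 Alpha Tibia group will be compared to the mean estimate of the control group", which is 43.48 points. An allowance of 4.23 points gives the limit of 39.25. The hypothesis table in the same section is looser. Its null reads "Central tendency of A is inferior to the central tendency of B", with no parameter named.

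The test is then left open and depends on how the data are distributed and on whether they pass a normality check. The plan states that "either the parametric one-sample t-test or the non-parametric one-sample sign test will be used to compare the 12 months post-operative SF-36 PCS result", and the comparison value is 39.25. SAP 3.1.1 and SAP 6.6 (Table 6.6.1) repeat this. SAP 4.10 makes the move to non-parametric methods general and rules out transformation. CIP 11.3.1 names Shapiro-Wilk as the normality test.

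CIP 11.1 gives the background. The limit is the lower bound of a 90% confidence interval around five pooled subgroup means. The SD is twice a published value and "was used for the sample size calculation (2 * 6.52 = 13.04 points"). The power statement is "With the proposed sample size of 61 subjects, the clinical investigation will have power of 80.0% to yield a statistically significant result", for a population mean of 43.48 tested against 39.25. The section adds: "For the clinical investigation the one-sided 95% confidence interval will be applied". It also explains why one source was left out of the pool. Among the reasons, that source "reported median score values whereas the other authors reported means". The section goes on to warn about mixing the two: "As summary score results usually tend to deviate from normality, means and medians might differ significantly".

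**The concern.** A one-sample sign test against 39.25 asks whether more than half of the subjects score above 39.25. That is a question about the median. The benchmark, the allowance and the limit are all statements about means, and neither document gives a median benchmark. The hypothesis table leaves the parameter open but does not supply a median limit.

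CIP 11.1 counts the reporting of medians as one reason not to mix a source with these means. The fallback then sets a median against a limit made of means. The same section expects summary scores to depart from normality, so the sign-test branch is a realistic outcome.

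This is the only endpoint with a hypothesis pair, an acceptance limit and a power calculation. If the data are skewed, either the chance of a false non-inferiority claim rises or power falls, depending on the direction of skew. The final report could also show a sign test and a confidence bound of the mean that disagree. As written the sign test would decide, although CIP 11.1 says the confidence interval applies.

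**Working it through.** **Inputs (CIP 11.1 and 11.3.2).** Subgroup means 38.00, 46.00, 40.80, 49.41, 43.21; assumed true mean 43.48; limit 39.25; SD 13.04; one-sided alpha 0.05; n = 61. I also use n = 64, which is 80 enrolled less 20% drop-out (80 x 0.80).

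**1. The plan's limit.** Mean = 217.42/5 = 43.484; SD 4.438; SE = 4.438/√5 = 1.985. Lower bound = 43.484 - 2.132 x 1.985 = 39.25. This matches the plan and uses means only.

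**2. The plan's power.** One-sample t-test, noncentrality 4.23 x √61/13.04 = 2.53 on 60 df: power 0.805, matching the SAP's software output. At n = 64 it is 0.822. The stated size is the t-test size.

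**3. The sign test alone, normal data (reference only).** P(score > 39.25) = Φ(4.23/13.04) = 0.627.
- n = 61: reject at 38 or more above the limit; exact alpha 0.036, power 0.584.
- n = 64: reject at 40 or more; alpha 0.030, power 0.570.

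This is not the power of the planned rule, which uses the sign test only after a switch.

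**4. The planned two-stage rule.** Shapiro-Wilk p ≤ 0.05 leads to the exact sign test, otherwise to the t-test. The plan gives no cut-off for the switch, so its general 0.05 level (CIP 11) is assumed. The skewed shapes are also assumptions: gamma distributions, reflected for left skew, scaled to SD 13.04. There were 20,000 simulated trials per cell, with simulation error about 0.3 percentage points. Entries are the percentage declared non-inferior, n = 61 / n = 64.

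| Shape | True mean | Planned rule | t-test alone | Switch fires |
|---|---|---|---|---|
| Normal | 39.25 | 5.1 / 5.1 | 5 (nominal) | about 5% |
| Normal | 43.48 | 79.5 / 81.3 | 80.5 / 82.2 | about 5% |
| Skewness -0.5 | 39.25 | 9.8 / 8.9 | 6.1 / 5.9 | 27-28% |
| Skewness -1 | 39.25 | 22.2 / 20.5 | 6.5 / 6.2 | 79-81% |
| Skewness +0.5 | 43.48 | 67.9 / 68.5 | 81.9 / 83.6 | 27-28% |
| Skewness +1 | 43.48 | 32.9 / 31.0 | 82.8 / 84.9 | 79-81% |

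Symmetric heavy tails (t with 5 df) give error 4.6% / 4.3% and power 81.1% / 81.4%. At n = 64, skewness -0.3 gives error 6.6% and skewness +0.3 gives power 76.5%.

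**5. Why the direction matters.** With left skew the median lies above the mean. At skewness -1 and SD 13.04 the gap is 2.14 points, and 2.14/4.23 is about half the allowance. A mean exactly at the limit then has a median of 39.25 + 2.14 = 41.39, and the sign test tends to reject. Right skew reverses this: error stays below 5% and power falls.

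**6. The SD.** At the published, undoubled 6.52, power is at least 95% in every shape tried. With the mean exactly at the limit, both tests and Shapiro-Wilk are unaffected by scale, so the left-skew error remains: 9.2% / 8.8% at -0.5 and 22.2% / 21.0% at -1.

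**7. Conflicting results among switched trials (SD 13.04).** At skewness -1 and true mean 39.25, 19.5% / 17.7% have a significant sign test while the one-sided 95% lower bound of the mean is below 39.25. At skewness +0.5 and true mean 43.48, 53% / 56% show the reverse.

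**The case against.** The damage depends on a shape that the documents do not give. They say that summary scores tend to be non-normal, but not in which direction. Normal and symmetric heavy-tailed data do almost no harm, and right skew only makes the rule conservative. The 22% needs a skewness of -1, the edge of the range tried.

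The doubled SD also flatters the figures. At 6.52 the gap between median and mean at skewness -1 is 1.07 points, a quarter of the allowance, and the power losses largely vanish. The error at that SD also falls quickly below the limit: with a true mean one point below 39.25 it is about 4%. In practice the limit is softened by about a point or less.

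The rule is also pre-specified and run once, and the final report will show the mean, the median and a confidence interval, so a conflict would be visible. Against a median of 39.25 the sign test is valid. The omitted source was dropped mainly for its unexplained scoring method and much higher values, so the parallel with the fallback is partial.

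All of this stands as a limit on size. It does not remove the defect. Naming two tests in advance does not name one parameter, and a visible conflict is not a resolved one. The sign test is valid only for a median hypothesis, for which the plan has no limit.

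**Conclusion.** The concern holds, and the rule should be corrected before the primary analysis. The documents define and size a test of the mean, then allow the data to replace it with a test of the median against the same number.

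The consequence is conditional, and only one property fails at a time. Under left skew the false non-inferiority rate at the limit rises to about 9-10% at skewness -0.5 and 20-22% at -1, with no loss of power. Under right skew power falls to about 68% at +0.5 and 31-33% at +1, with error below 5%. With normal data nothing material is lost. These figures rest on gamma shapes, a switch at Shapiro-Wilk p ≤ 0.05 and, for the power losses, SD 13.04. How often the switch would fire in this trial cannot be derived from the documents.

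**What to change.** - **Primary test.** In CIP 11.3.2, SAP 3.1.1 and SAP 6.6 (Table 6.6.1), specify the one-sample t-test of the mean against 39.25 whatever the Shapiro-Wilk result. Equivalently, require the one-sided 95% lower confidence bound of the mean to be at or above 39.25.
- **Hypotheses.** In both hypothesis tables, name the mean in place of central tendency.
- **Sensitivity.** Add a studentised bootstrap lower bound for the mean. At skewness -1 and n = 64 its error is 5.2%, against 6.6% for the t-test and 6.9% for the percentile bootstrap (3,000 trials, 999 resamples each; simulation error 0.4-0.5 points).
- **Sign test.** Keep it as supportive only, labelled as a statement about the median.
- **SAP 4.10.** Add an exception for the primary endpoint, leaving the general rule for other comparisons such as the paired tests in SAP 6.7.1.

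The cost is CIP and SAP wording. The calculated 61 evaluable subjects stand, and no extra patients or data are needed.
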